3. PATIENT SELECTION

3.1 Eligibility Criteria

The eligibility criteria listed below are to be interpreted literally and cannot be waived. No exceptions will be given. All clinical and laboratory data required to determine eligibility of a patient enrolled on this trial must be available in the patient's medical or research record.

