3.1.6 Organ Function

Patients must have normal organ and marrow function documented within 14 days of registration and within 7 days of the start of treatment as defined below:

- $>1,000/mm^{3}$ Absolute neutrophil count _
- >100,000/ mm³ (unsupported) – Platelets
- Hemoglobin >10g/dl (unsupported
- Total bilirubin ≤ 1.5 times upper limit of normal (ULN) for age
- <5 x institutional upper limit of normal for age - ALT(SGPT)
- Albumin $\geq 2g/dl$
- Creatinine clearance or radioisotope GFR ≥ 70 mL/min/1.73 m² or Serum creatinine based on age/gender as follows:

	Table 8					
Serum Creatinine for age/gender						
Age	Maximu Creatinin	m Serum e (mg/dL)				
	Male	Female				
1 to $<$ 2 years	0.6	0.6				
2 to < 6 years	0.8	0.8				
6 to < 10 years	1	1				
10 to < 13 years	1.2	1.2				
13 to < 16 years	1.5	1.4				
\geq 16 years	1.7	1.4				
The threshold creatinine va	lues in this Table were	derived from the				
Schwartz formula for estim	ating GFR (Schwartz e	t al. J. Peds,				
106:522, 1985) utilizing child length and stature data published by the						
CDC.		-				

T 11 0

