5.1.3.1 Intra-patient Dose Escalation of TMZ during Maintenance

In an effort to maximize the TMZ dose (and potentially the efficacy of the combination treatment) that can be administered with ABT-888 for each patient, **intra-patient dose escalation of TMZ will be studied only for patients with minimal toxicities, considered at least possible related, in each course.** These patients' TMZ dose will be escalated (per Table 12) to 175 mg/m²/day (Dose Level 2), and subsequently to 200 mg/m²/day of TMZ (Dose Level 3) if the toxicities observed after 1 course of protocol therapy at each dose level meet the defined criteria. In patients who are not eligible to dose escalate after course 1 due to greater than minimal toxicities, there will be no further attempts to escalate the dose of temozolomide. Patients eligible to dose escalate after course 1 but are not dose escalated due to site related issues may start dose escalation in a subsequent course provided they meet all criteria for dose escalation.

Dose escalation of TMZ is not allowed if any of the following conditions exist:

Hematological Toxicity

- > Grade 1 thrombocytopenia
- > Grade 2 neutropenia

Non-hematologic Toxicity

- Any grade 4 non-hematologic toxicity
- Any grade 3 non-hematologic toxicity with the exception of:
 - \circ Grade 3 nausea and vomiting of < 5 days
 - Grade 3 elevation of transaminases that returns to levels meeting eligibility criteria within 7 days of study drug interruption and does not recur upon restarting drug.
 - Grade 3 fever or infection of fewer than 5 days in duration
 - o Grade 3 hypophosphatemia, hypokalemia, hypocalcemia or
 - o hypomagnesemia responsive to oral supplementation
- Any grade 2 non-hematologic toxicity that persists for > 7 days and is considered medically significant or sufficiently intolerable by patients that requires treatment interruption.

Intra Patiant Dasa Escalati	Intra-Patient Dose Escalation of TMZ during Maintenance Therapy (Days 1-5 per 28 day cycle)								
Dose Level									
0	20 mg/m ² BID	135 mg/m ² /day							
1 (Starting Dose)	25 mg/m ² BID	135 mg/m ² /day							
2	25 mg/m ² BID	$175 \text{ mg/m}^2/\text{day}$							
3	25 mg/m ² BID	$200 \text{ mg/m}^2/\text{day}$							

Table 12

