6.2.1 Non-Hematologic Toxicity

- Any grade 4 non-hematologic toxicity
- Any grade 3 non-hematologic toxicity with the exception of:
 - \circ Grade 3 nausea and vomiting of < 5 days
 - Grade 3 elevation of transaminases that returns to levels meeting eligibility criteria within 7 days of study drug interruption and does not recur upon restarting drug.
 - Grade 3 fever or infection of fewer than 5 days in duration
 - Grade 3 hypophosphatemia, hypokalemia, hypocalcemia or hypomagnesemia responsive to oral supplementation
- Any grade 2 non-hematologic toxicity that persists for > 7 days and is considered medically significant or sufficiently intolerable by patients that requires treatment interruption

For any of the above non-hematologic toxicities during maintenance therapy, ABT-888 and TMZ will be withheld until the toxicity resolves to meet on study parameters (section 3.1.6), and the patient will restart ABT-888 and TMZ at the next lower dose level (see **Table 12**). Protocol therapy will be discontinued if a non-hematologic dose modifying toxicity occurs at dose level 0.

- 6.2.2 Hematological Toxicity
 - \geq Grade 3 thrombocytopenia
 - Grade 4 neutropenia
 - A delay of > 14 days in starting subsequent cycles of maintenance due to ANC < 1,000/mm³ and/or platelet < 100,000/mm³ (for example, a patient never experienced grade 3 thrombocytopenia, but his/her platelet count lingered between 50,000 to 100,000/ mm³ beyond 42 days after the start of the previous course of maintenance therapy)

For the hematologic toxicities outlined above that occur during maintenance therapy, ABT-888 and TMZ will be withheld until criteria described below are met, and ABT-888 and TMZ will be restarted at the next lower dose level (see **Table 12**). Protocol therapy will be discontinued if a hematologic dose-modifying toxicity occurs at dose level 0.

- a. \geq Grade 3 thrombocytopenia: Platelet transfusion is permissible and strongly encouraged for patients with dose-limiting thrombocytopenia to minimize risk of intra-tumoral hemorrhage. ABT-888 and TMZ should not be restarted until platelet count has recovered to \geq 100,000/mm³ (transfusion independent).
- b. Patients with grade 4 neutropenia may receive filgrastim (G-CSF) support only for documented infection and/or sepsis. ABT-888 and TMZ should not be restarted until the

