10. STUDY CALENDAR

		r	Fable 1	8				
	Standard (linical and l	Laborator	y Assessmen	ts – Phase I			
	Pre- therapyABT888 and Radiation (Course 1.1)Maintenance (Courses 2.1 – 2.23)				End of Treatment			
PHYSICAL ASSESSMENTS		ABT 888 + RT	Rest Period	Week 10 - 11 ¹⁰	Weekly Courses 1-10	Prior to Courses 2-10	Extended Therapy Courses 11-23	
Medical history, physical exam and diary review	Х	Weekly	X9	Х		Х	X ¹²	Х
Vital signs	Х	Weekly	X ⁹	Х		Х	X ¹²	Х
Performance status	Х	Weekly	X ⁹	Х		Х	X ¹²	Х
Neurologic exam	Х		X ⁹	Х		Х	X ¹²	Х
Height, Weight, BSA	Х		X ⁹	Х		Х	X ¹²	
LABORATORY EVALUATIONS								
CBC (WBC, Hgb, Hct, Platelets, ANC, ALC)	Х	Weekly ¹	X ⁹	Х	\mathbf{X}^1		X ¹³	Х
Serum Chemistry (Electrolytes, BUN, Creatinine, Calcium, Magnesium, Phosphorous, SGOT(AST), SGPT(ALT), Total Bilirubin, Albumin)	Х	Weekly ²	X ⁹	х		X ²	X ¹³	Х
Pregnancy test ³	Х			Х		Х	Х	
IMAGING ASSESSMENTS								
Brain MRI	X^4			X^4		X ^{4,11}	X^{14}	X^{11}
MRI Perfusion/Permeability	X^4			X^4		X 4,11		X^{11}
Diffusion Tensor Imaging (DTI)	X^4			X^4		X 4,11		X ¹¹
Correlative Studies								
Pharmacokinetic Studies ⁵	Х	Х						
Biology Study (PARP,NHEJ and γ H2AX) in PBMC's ⁶	Х	Х			X^6			
Biology study – pre-trial tumor material	X^7							
Urine Biomarker ⁸	Х			Х		X ⁸		

 CBC is done weekly for all courses. Patients with dose limiting hematologic toxicity (≥Grade 3 thrombocytopenia or Grade 4 neutropenia) should have CBC at least twice weekly (3-4 days apart) until toxicities improve to grade 2 or less

2. Patients with grade 3 or 4 non-hematologic toxicity should have relevant laboratory tests repeated twice weekly (3-4 days apart) until they recover to grade 2 or less

3. Serum or urine pregnancy test is to be repeated within 72 hours prior to enrollment in females of childbearing potential and prior to each course during maintenance

- 4. Neuroimaging assessments are to be completed within 2 weeks of registration, at the end of radiation + ABT888, (week 10-11), within 1 week prior to courses 3, 5, 8 and at the end of maintenance. See footnote #11 for details of investigational imaging procedures. For patients with possible tumor progression on week 10, 18, or 26 imaging studies, see guidelines in section 2.4.2 or 11.1.4 for frequency of next imaging study.
- Participation in the pharmacokinetic study is required for the Phase I portion of the study. See section 9.1.1 for collection schedule

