Height, Weight, BSA	Х		X9	Х		Х	X ¹²	
LABORATORY EVALUATIONS								
CBC (WBC, Hgb, Hct, Platelets, ANC, ALC)	Х	Weekly ¹	X ⁹	Х	\mathbf{X}^{1}		X ¹³	Х
Serum Chemistry (Electrolytes, BUN, Creatinine, SGOT(AST), SGPT(ALT), Total Bilirubin,)	Х	Weekly ²	X ⁹	Х		X ²	X ¹³	Х
Pregnancy test ³	Х			Х		Х	Х	
IMAGING ASSESSMENTS								
Brain MRI	X^4			X^4		X ^{4,11}	X^{14}	X^{11}
MRI Perfusion/Permeability	X^4			X^4		X 4,11		\mathbf{X}^{11}
Diffusion Tensor Imaging (DTI)	X^4			X^4		X ^{4,11}		X^{11}
Correlative Studies								
Pharmacokinetic Studies ⁵	Х	Х						
Biology Study (PARP,NHEJ and γH2AX) in PBMC's ⁶	Х	Х			X^6			
Biology study – Pre-trial tumor material ⁷	X							
Urine Biomarker ⁸	Х			Х		X ⁸		

Table 19

1. CBC is done weekly for all courses. Patients with dose limiting hematologic toxicity (≥Grade 3 thrombocytopenia or Grade 4 neutropenia) should have CBC at least twice weekly (3-4 days apart) until toxicities improve to grade 2 or less

2. Patients with grade 3 or 4 non-hematologic toxicity should have relevant laboratory tests repeated twice weekly (3-4 days apart) until they recover to grade 2 or less

3. Serum or urine pregnancy test is to be repeated within 72 hours prior to enrollment in females of childbearing potential and prior to each course during maintenance

4. Neuroimaging assessments are to be completed within 2 weeks of registration, at the end of radiation + ABT888, (week 10-11), within 1 week prior to courses 3, 5, 8 and at the end of maintenance. See footnote #11 for details of investigational imaging procedures. For patients with possible tumor progression on week 10, 18, or 26 imaging studies, see guidelines in section 2.4.2 or 11.1.4 for frequency of next imaging study.

5. Participation in the pharmacokinetic study is optional for the Phase II portion of the study. See section 9.1.1 for collection schedule

6. Participation in the correlative biology study in PBMC's is **optional.** See section 9.1.2 9.1.2 for collection schedule

- 7. Participation in the correlative biology study pre-trial tumor material is optional. See Section 9.1.3 for processing and shipping instructions
- 8. Participation in the urine correlative study is optional. Urine samples should be collected at the time of each scheduled MR (section 9.1.4)
- 9. During the rest period, each patient should have at least one visit between weeks 7 and 10.
- 10. Laboratory tests and assessments may be completed ± 1 week of week 10, prior to starting Maintenance.

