25 mg/m² ABT-888 and 135 mg/m² of TMZ with a possibility to escalate to 175 mg/m² and to 200 mg/m² of TMZ, if no unacceptable toxicities occur following 1 course of treatment at each of these dose levels (**Table 12**). More specifically, intra-patient dose escalation will only be considered if a patient meets the escalation criterion following the first course of TMZ as part of maintenance therapy. Intra-patient dose escalation will be assessed only in patients who are eligible to escalate and escalation to a given dose will be halted based on similar rules employed in traditional 3+3 designs, i.e. if 2 out of first 2-6 patients, 4 out of first 12 patients, etc. experience dose modifying toxicities during their first course of therapy at a given dose level. . This stopping rule will be applied for patients enrolled during the Phase I and Phase II components of the study. Even though these stopping rules will only be enforced during the first course of treatment at a given dose level for TMZ, we will periodically monitor for the occurrence of dose modifying toxicities in later courses and may revise this approach in the event that excessive toxicities are observed.

13.2 Phase II Study Design/Endpoints:

The primary efficacy endpoint of this phase II trial is overall survival defined as the time from initiation of therapy to the date of death from any cause or to the date patient was known to be alive for surviving patients. Progression-free survival (PFS) is a secondary endpoint and is defined as the time from initiation of treatment to the earliest date of failure (disease progression, death from any cause, or second malignancy) for patients who fail and to the last assessment date for patients who have not failed. Patients who start other anti-cancer therapy prior to disease progression will be censored in the Kaplan-Meier estimate of PFS as of the date the alternative therapy began. Patients who have not failed (died) at the time of analyses will be censored at their last date of contact in the Kaplan-Meier estimate of the PFS (overall survival) distribution.

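### The Phase II calendar (Table 19) does not schedule calcium, magnesium or phosphorus, although the TMZ escalation, dose-modification and halting rules count toxicities in all three

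*Combined protocol and SAP*

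**What the plan says.** Section 10 gives each phase its own calendar. The Phase I chemistry row (Table 18) reads "Serum Chemistry (Electrolytes, BUN, Creatinine, Calcium, Magnesium, Phosphorous, SGOT(AST), SGPT(ALT), Total Bilirubin, Albumin". The Phase II row (Table 19) reads "Serum Chemistry (Electrolytes, BUN, Creatinine, SGOT(AST), SGPT(ALT), Total Bilirubin", followed by a stray comma. The time points are identical.

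The maintenance rules do not differ by phase. Section 5.1.3 is headed for both. Under 6.2.1, any grade 4 non-hematologic toxicity is dose-modifying, and so is any grade 3 apart from listed exceptions, if at least possibly attributable to treatment. One exception is "Grade 3 hypophosphatemia, hypokalemia, hypocalcemia or hypomagnesemia responsive to oral supplementation". Section 5.1.3.1 uses the same exception ("Grade 3 hypophosphatemia, hypokalemia, hypocalcemia or" hypomagnesemia, split over two bullets) when it defines what bars TMZ escalation. Section 13.1.3 halts escalation to a TMZ level when enough children have dose-modifying toxicities in their first course at that level (2 of the first 2-6, 4 of the first 12, and so on), and adds: "This stopping rule will be applied for patients enrolled during the Phase I and Phase II components of the study".

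On albumin, 3.1.6 sets a minimum of 2 g/dl under the heading "Patients must have normal organ and marrow function documented within 14 days of registration and within 7 days of the start of treatment", and 3.1 states: "The eligibility criteria listed below are to be interpreted literally and cannot be waived".

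**The concern.** Feasibility of intra-patient TMZ escalation is a Phase II primary objective (1.2). The rules that decide it depend partly on three laboratory values that the Phase II calendar does not ask for. A child with low phosphate, calcium or magnesium severe enough to count, but without symptoms, could be escalated, or left out of the halting count, because nobody measured it. Sites that order the fuller panel by habit would find such events and others would not. The halting rule pools children from both phases, so its count would also mix children tested on schedule with children tested at discretion.

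**Working it through.** There is no plan figure to reproduce. The check sets the texts side by side and then counts reach and cost.

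**1. What is missing.** The Table 18 panel minus the Table 19 panel is calcium, magnesium, phosphorus and albumin. Reading electrolytes in Table 19 to include the minerals is unsafe, because Table 18 lists them in addition to electrolytes. Potassium, the fourth analyte in the exception, is plausibly covered. The minerals are missing from mid-list and albumin from the end, which looks more like editing than damage in text extraction.

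**2. What the rules need.** A mineral event counts if it is grade 4, or grade 3 not responsive to oral supplementation, and at least possibly drug-related. For a child who escalates without delay:

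| Draw | Decision it informs |
|---|---|
| Before course 2 | Bar on moving to TMZ 175 mg/m²/day |
| Before course 3 | Halting count at 175; bar on moving to 200 |
| Before course 4 | Halting count at 200 |

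The dose-modification rule in 6.2.1 continues through later courses.

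**3. Whether another provision supplies the test.**
- Table 19 footnote 2 repeats relevant tests twice weekly, but only once a grade 3 or 4 toxicity is known.
- The calendar note allowing other studies when clinically indicated does not reach a silent abnormality.
- Weekly testing in maintenance is CBC only.
- Section 13.1.3 says "we will periodically monitor for the occurrence of dose modifying toxicities in later courses and may revise this approach". That review, like the DSMB's, sees only what was measured.

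**4. Albumin.** Section 3.5 requires all eligibility tests within 14 days before registration, so a baseline value is mandatory. What remains is smaller. Section 3.1.6 also asks for documentation within 7 days of starting treatment, but the repeat list in 3.5 (CBC, bilirubin, ALT, creatinine) omits albumin. Hepatic function must meet on-study criteria before maintenance (5.1.3), and restart after a non-hematologic toxicity refers back to 3.1.6 (6.2.1). Table 19 names albumin at neither the pre-therapy nor the week 10-11 draw.

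**5. Reach.** Phase I children treated at the recommended dose count toward the 60 (13.2).
- If six carry over: 60 − 6 = 54, and 54/60 = 90%. This fits the Table 21 total if Phase I enrols 12: 12 + 60 − 6 = 66.
- If twelve carry over: 60 − 12 = 48, and 48/60 = 80%.

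Both counts are before drop-outs.

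**6. Chemistry draws for a Phase II child who completes 10 courses.** Pre-therapy 1 + weekly in radiation 6-7 + rest period at least 1 + week 10-11 1 + before courses 2-10 9 + end of treatment 1 = 19-20. The count is 18 if the pre-therapy draw serves as day 1 and radiation lasts six weeks. None of these draws names the four analytes.

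**The case against.** The minerals appear in the rules only inside an exemption. The operative rule covers any grade 3 or 4 non-hematologic toxicity, and no calendar tests for all of those. The events left uncovered are narrow: severe or refractory, drug-related and silent. The temozolomide toxicity table (Table 14) lists no mineral disturbance. The PBTC-027 account in 2.2.3 describes hematologic dose-limiting toxicities and serious CNS events. Pre-course chemistry, about four weeks after a five-day treatment, would miss a transient fall even under Table 18. The panel may also have been cut deliberately; the visible text gives no reason, but parts of the document were not available.

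Much of this stands, and it limits the size of the point. It does not remove the mismatch: the protocol singles out these abnormalities for grading and tests for them on schedule in one phase only. The ABT-888 adverse event list is not in the available text, so the drug's own mineral risk cannot be judged either way. The limit of pre-course timing is the same in both phases; the missing analytes are not.

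A reader might infer that a Phase II child could properly be registered without an albumin result. Sections 3.1, 3.1.6 and 3.5 rule that out. A reader might also infer that the halting rule or the feasibility result is unreliable. The documents give no event rate to support that, and sites may be running these tests anyway.

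**Conclusion.** The point holds as a minor inconsistency between the Phase II calendar and the toxicity rules. Silent countable mineral events may be missed in Phase II, and ascertainment differs between the pooled phases. The effect is probably small: expected toxicity is hematologic with weekly CBC, grade 3 changes that respond to oral supplements are exempt, and the first children at each escalated TMZ level probably come largely from Phase I. Its size cannot be derived from the documents, and no change in halting probability is claimed. Overall survival, sample size and power are unaffected. The conclusion assumes that sites follow Table 19 as written and that electrolytes has the same meaning in both tables. Albumin is a smaller matter of consistency.

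**What to change.** Replace the Table 19 chemistry row with the Table 18 row, at the time points already scheduled. This adds four analytes: 4 × 18 = 72 to 4 × 20 = 80 results per child who completes 10 courses.

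If the shorter panel is intended, state why and keep a minimum: calcium, magnesium and phosphorus before courses 2, 3 and 4, and albumin at pre-therapy and week 10-11. That is 3 × 3 + 2 = 11 results per child. If escalation is delayed, the mineral tests should follow the first course at each TMZ level. This version leaves the dose-modification rule without scheduled mineral tests in later courses.

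Neither option needs a new visit. The costs are possibly slightly more blood per draw, a wider order at outside laboratories (allowed by 3.4), and more mild abnormalities to grade and attribute.

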11. MEASUREMENT OF EFFECT

11.1 Tumor Response Criteria

11.1.1 Complete Response (CR)

Complete disappearance on MR/CT of all enhancing tumor and mass effect, on a stable or decreasing dose of corticosteroids (or receiving only adrenal replacement doses), accompanied by a stable or improving neurologic examination, and maintained for at least 8 weeks.

11.1.2 Partial Response (PR)

Greater than or equal to 50% reduction in tumor size by bi-dimensional measurement, as compared with the baseline measurements, on a stable or decreasing dose of corticosteroids, accompanied by a stable or improving neurologic examination, and maintained for at least 8 weeks

11.1.3 Stable Disease (SD)

Neurologic exam is at least stable and maintenance corticosteroid dose not increased, and MR/CT imaging meets neither the criteria for PR nor the criteria for Progressive Disease. If this category is to be reported as of possible clinical benefit, Stable Disease status must be maintained for 16 weeks.

11.1.4 Progressive Disease (PD)

Progressive Disease (PD): Progressive neurologic abnormalities or worsening neurologic status not explained by causes unrelated to tumor progression (e.g., anticonvulsant or corticosteroid toxicity, electrolyte disturbances, sepsis, hyperglycemia, etc.), OR a greater than 25% increase in the bi-dimensional measurement, taking as a reference the smallest disease measurement recorded since the start of protocol therapy, OR the appearance of a new lesion, OR increasing doses of corticosteroids required to maintain stable neurological status or imaging.

* Consideration for possible pseudo-progression

For patients showing possible radiographic evidence of tumor progression on MRI during the first 6 months after initiation of ABT-888 and radiation (on required MRI studies performed at week 10, week 18, or 26), the treating physician will have the option of allowing the patient to remain on study, continuing protocol therapy, and repeating disease reassessment in 4-6 weeks. Provided that the patient does not show clinical deterioration consistent with tumor progression, has been on a stable or declining dose of steroids, and the subsequent MRI demonstrates tumor regression or stable disease, then the patient will remain on study and continue protocol therapy, and the frequency of subsequent MRI will revert to pre-specified intervals. If the repeat MRI after 4-6 weeks shows disease progression, rather than pseudo-progression, then the time of progression will be the date of the initial MRI, not the follow up scan. The addition of steroids is allowed, at the time of suspected pseudo-progression, as long as the patient can be maintained on a decreasing dose.

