2.4.2 Rationale for Imaging Studies

If ABT-888 is effective in enhancing radiation effect in DIPG as we hypothesize, it is possible that the rate of pseudoprogression may be higher for this proposed study compared to historical series. In parallel with earlier pediatric DIPG trials, for patients showing possible tumor progression on MRI during the first 6 months after the initiation of ABT-888 and irradiation (on required MRI studies performed at weeks 10, week 18, or 26), the treating physician will have the option of allowing the patient to remain on study, continuing protocol therapy, and repeating disease reassessment in 4-6 weeks. Provided that the patient does not show clinical deterioration consistent with tumor progression, has been on a stable or declining dose of steroids, and the subsequent MRI demonstrates tumor regression or stable disease, then the patient will remain on study and continue protocol therapy, and the frequency of subsequent MRI will revert to prespecified intervals. If the repeat MRI after 4-6 weeks shows disease progression, rather than pseudo-progression, then the time of progression will be the date of the initial MRI, not the follow up scan.

Key to assessing disease course and potential pseudoprogression is inclusion of detailed clinical data documenting each patient's status at the time of scheduled imaging or upon institutional call of "progressive disease." The ability to track neurologic status, symptoms or signs potentially heralding or reflecting progressive disease, or apparent neurologic stability is important in correlating clinical status with imaging findings, and documenting the clinical and/or imaging findings that prompt the investigator to call "progressive disease." We recently documented a relationship between tumor volume and diffusion (measured by serial echoplanar diffusion imaging) prior to and immediately after irradiation in a cross-protocol analysis of prior PBTC newly diagnosed DIPG patients. Tumors with larger diffusion values seemed to respond early to radiation therapy and percent reduction in ADC values correlated with both progression-free and overall survival rates.¹⁸ Tracking MR imaging volumetric, serial findings in the context of a phase II study of tipifarnib and irradiation showed pseudoprogression in just one of the 40 patient's studied.¹⁹

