5.3.1 Steroids

Corticosteroids should be used at the lowest dose to control symptoms of edema and mass effect, and discontinued, if possible.

5.3.2 Anticonvulsants Anticonvulsants should be used, if indicated.

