5.3.6 Concomitant Therapy

Other anti-cancer or experimental agents or therapies are not permitted.

5.4 **Duration of Therapy**

In the absence of treatment delays due to adverse event(s), treatment may continue for 10 cycles. See section 2.4.2 or 13.2.1 for guidelines on possible pseudo-progression on MRIs performed at weeks 10, 18, and 26. All patients will conclude protocol based therapy at the completion of 10 cycles of maintenance treatment. At the end of protocol defined therapy, the patient should complete all end of treatment assessments.

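### A patient whose steroids are started or raised at suspicion of pseudoprogression and then tapered can be classed either as progression (off treatment, PFS event) or as pseudoprogression

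*Combined protocol and SAP*

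**What the plan says.** - **PD, Section 11.1.4.** The criteria are alternatives joined by OR. One of them is "increasing doses of corticosteroids required to maintain stable neurological status or imaging".
- **Pseudoprogression, same section.** After a suspicious required MRI at week 10, 18 or 26, the physician may continue protocol therapy and reassess in 4-6 weeks. The patient stays on study if there is no clinical deterioration consistent with progression and the patient "has been on a stable or declining dose of steroids, and the subsequent MRI demonstrates tumor regression or stable disease". If the repeat MRI shows progression, it is dated to the initial MRI.
- **Last sentence of 11.1.4.** "The addition of steroids is allowed, at the time of suspected pseudo-progression, as long as the patient can be maintained on a decreasing dose".
- **SD, Section 11.1.3.** "Neurologic exam is at least stable and maintenance corticosteroid dose not increased", among other conditions.
- **Section 2.4.2.** It gives the same pseudoprogression rule, including the steroid condition, but not the permission to add steroids.
- **Section 13.4.1.** True versus pseudo progression is decided on tumor measurements from later scans. A 95% confidence interval is planned for the pseudoprogression proportion. Steroids are not mentioned.
- **Consequences.** PD under 11.1.4 takes the patient off treatment (5.5.1) and is a PFS event (13.2). The pseudoprogression proportion is a primary objective of Phase I (1.1) and Phase II (1.2).
- **Cross-reference, Section 5.4.** "See section 2.4.2 or 13.2.1 for guidelines on possible pseudo-progression on MRIs performed at weeks 10, 18, and 26". Section 13.2.1 defines evaluable patients and says nothing on pseudoprogression.
- **Steroid use.** Section 5.3.1 says "Corticosteroids should be used at the lowest dose to control symptoms of edema and mass effect". Section 5.3 asks only that use be recorded.

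**The concern.** Adding steroids is a foreseeable response to a suspicious scan in this disease, and the protocol provides for it. The same act is also evidence of progression under one rule, possibly disqualifying under a second, permitted under a third and ignored by the analysis rule. If the sections are not aligned, the classification of such a patient depends on which text is applied.

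There is also a direction to the possible bias. The PD wording accepts that steroids may be needed to keep imaging stable. A stable repeat MRI after steroids were added therefore does not by itself separate pseudoprogression from progression held in check by the steroid. Because 13.4.1 looks at measurements alone, masked progression would be counted as pseudoprogression and as continuing PFS. The rule that dates progression to the initial MRI would not correct this, because it applies when the 4-6 week repeat scan shows progression, and in this scenario it does not.

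**Working it through.** There is no stated design figure to reproduce, so the check is one worked case set against each rule, followed by a calculation of scale.

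**Worked case.** The week 10 MRI suggests progression. Steroids are started to keep the patient neurologically stable and are then tapered. There is no clinical deterioration consistent with progression. The repeat MRI at 4-6 weeks shows no growth.

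| Rule | Result |
|---|---|
| PD criterion, 11.1.4 | Progression: off treatment, PFS event |
| SD definition, 11.1.3 | Stable disease not available if the dose counts as increased |
| Steroid condition, 2.4.2 and 11.1.4 | Not met if the window includes the start of steroids; met if judged over the taper only; no window stated |
| Last sentence, 11.1.4, read as an exception | Pseudoprogression: stays on treatment, no PFS event |
| Section 13.4.1 | Pseudoprogression, on measurements alone |

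The SD row matters because the pseudoprogression rule accepts regression or stable disease on the repeat MRI, and stable disease carries its own steroid condition. The rules give opposite answers, and nothing in the text ranks them.

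**Scale.** Inputs: about 60 Phase II patients (13.3), and one pseudoprogression among 40 patients in the earlier phase II study of tipifarnib and irradiation (2.4.2), the only rate the documents cite. The number of patients who would receive steroids at suspicion is not given, so a range is shown.

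One patient = 1/60 = 1.7 percentage points.

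Exact (Clopper-Pearson) 95% limits for k of n are the 2.5% point of Beta(k, n−k+1) and the 97.5% point of Beta(k+1, n−k). Section 13.4.1 does not name an interval method; this one is my choice.

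| Cases | Proportion | Exact 95% CI |
|---|---|---|
| 1/40 (earlier study) | 2.5% | 0.1 to 13.2 |
| 1/60 | 1.7% | 0.0 to 8.9 |
| 3/60 | 5.0% | 1.0 to 13.9 |
| 4/60 | 6.7% | 1.8 to 16.2 |
| 6/60 | 10.0% | 3.8 to 20.5 |
| 12/60 | 20.0% | 10.8 to 32.3 |

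For illustration, if three patients changed class, 1/60 would become 4/60, a move of 3/60 = 5.0 points. Without earlier censoring, the same three would move the PFS curve by 5.0 points at the time of the disputed scan.

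**The case against.** The strongest reply is that the last sentence of 11.1.4 sits under the pseudoprogression consideration, directly below the PD definition, and reads naturally as a specific exception: add, then taper. Section 5.5.1 refers to PD as outlined in the whole of 11.1.4, which includes that consideration. This reading is reasonable. It narrows the problem to patients whose steroids are started or raised at suspicion and then tapered; a patient whose dose keeps rising is not covered by the exception. It does not remove the problem, because the override is not stated and 11.1.3 and 2.4.2 are not aligned with it.

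Several stronger readings are tempting but not supported:

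- **That such a patient necessarily fails 2.4.2.** This depends on the unstated window. Section 2.4.2 is also a rationale section, while 11.1.4 holds the response criteria.
- **That the study calendar sends sites to conflicting steroid rules.** Footnote 4 cites 2.4.2 or 11.1.4 only for the frequency of the next imaging study, and on that the two agree.
- **That the site's reading alone decides the pseudoprogression proportion.** Section 9.2.5 provides central imaging review for response and pseudoprogression at study completion. That limits site variation but does not settle the matter, since the review is given no steroid rule.
- **That any steroid increase for edema during radiation is PD.** The criterion can be read that way, since the consideration covers only the week 10, 18 and 26 scans, but the documents do not state that this is intended. It calls for clarification only.
- **That a three-patient shift is to be expected.** No document gives such a count. The abstract also names 1-year PFS as the secondary measure, and masked progression recognized later within the year would leave the 1-year estimate unchanged.

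**Conclusion.** The concern holds for a defined subgroup: patients with a suspicious required MRI, without clinical deterioration consistent with progression, whose steroids are started or raised at suspicion and then tapered. For them the PD and SD definitions point to progression, while the last sentence of 11.1.4, read as an exception, and 13.4.1 point to pseudoprogression.

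What is affected is the pseudoprogression proportion, PFS, best response before progression and time on treatment. Each case is worth 1.7 points if about 60 patients are analyzed. The total effect cannot be stated because the number of cases is not given; if pseudoprogression is as rare as the cited 1 in 40, a few disputed cases could dominate the estimate. Overall survival, the stopping boundaries and the stated 87.72% power do not depend on this classification. It should be corrected, but it does not threaten the primary efficacy comparison.

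**What to change.** 1. **Reconcile 2.4.2, 11.1.3, 11.1.4 and 13.4.1.** The sponsor must state whether the last sentence of 11.1.4 overrides the steroid criterion for PD, and from which date a stable or declining dose is judged. It must also clarify how the PD criterion treats steroid increases during radiation. No clinical rule is proposed here.
2. **In 13.4.1 only, add an analysis flag.** Flag patients whose steroids were started or raised between the time of the initial suspicious MRI (same-day changes included) and the repeat MRI. Report their number. Give the pseudoprogression proportion with its 95% confidence interval, and the PFS estimate, with these patients counted each way. This does not bear on who stays on treatment.
3. **Correct the cross-reference in 5.4** from 13.2.1 to 11.1.4.

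The cost is wording in five sections, a small indeterminate group in the report and one sensitivity analysis. The flag needs steroid start and change dates. Section 5.3 says only that use is recorded, so the sponsor should confirm that the concomitant medication record holds those dates.
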